1.3.2.4 Study Drug Compliance

On Day 0 (baseline visit-Visit 2) and at Visit 3, Visit 4, and Visit 5, the study personnel will give to the Subject the biweekly kit containing two weeks of the study product and delivery kits. At Visits 3, 4, 5 and 6, patients will return the used or unused study boxes/vials to the clinic in the original carton. All Study Product returned by patients should be inventoried same day of return. Inventory will take place at Visits 3, 4, 5 and 6. Any discrepancies and/or deficiencies in study drug accountability must be recorded along with an explanation in the appropriate accountability log.

1.3.3 Efficacy Assessments

1.3.3.1 Fluorescein corneal staining

Following the instillation of fluorescein in the qualifying eye(s) grade (density) of the SPK will be determined at Visit 1, 2, 4, 6, 7 using the NEI (National Eye Institute [NEI]/Industry Workshop 0-15) scale of 0 to 3 for each of the five areas: Zone 1 Central, Zone 2 Superior, Zone 3 Temporal, Zone 4 Nasal, and Zone 5 Inferior.

Epithelial healing, defined as Grade 1 or absence of staining (Grade 0) in a previously qualifying zone, will be determined by the investigators and recorded on eCRF at Visit 4, 6, and 7.

1.3.3.2 Corneal Sensitivity Testing

Corneal Sensitivity will be measured (in cm) using a Cochet Bonnet aesthesiometer at Visit 1, 2, 4, 6, 7

1.3.3.3 Best Corrected Distance Visual Acuity (BCDVA)

The logarithm of the minimal angle of resolution (logMAR) visual acuity score (ranged from -0.3 to 1) and Snellen score (ranged from 20/10 - 20/200) will be recorded at Visit 1, 2, 4, 6, 7.

1.3.3.4 Tear Film Break-Up Time (TFBUT)

Tear film break-up time (sec) will be assessed using fluorescein at Visit 2, 4, 6, 7.

1.3.3.5 Schirmer Test (w/o Anesthesia)

Unanesthetized Schirmer's test measures the amount of wetting (mm) at Visit 2, 4, 6, 7.

1.3.3.6 Impact of Dry Eye on Everyday Life (IDEEL)

This 57-item questionnaire assesses dry eye impact at Visit 2, 4, 6, 7, and constitutes following 3 modules:

- Dry eye Quality of Life (27 questions) comprising three sections: "Daily activities", "Feelings" and "Work".
- Dry eye Treatment satisfaction & Bother (10 questions) comprising two sections: "Treatment In general" and "Treatment- Eye drop".
- Dry eye Symptom bother (20 questions).

1.3.3.7 EQ-5D-5L

The EQ-5D-5L is a standardized measure of health status developed by the EuroQol Group in order to provide a simple, generic measure of health for clinical and economic appraisal (Herdman et. al. 2011). This self-administered questionnaire consists of five dimensions (mobility, self-care, usual activities, pain/discomfort, and anxiety/depression) in a scale of 1 (no problems) to 5 (extreme problems) with high score favoring worse as well as the health today score in a scale of 0 (the worst health you can imagine) to 100 (the best health you can imagine) at Visit 2, 4, 6, 7.

1.3.3.8 Anterior Segment Optical Coherence Tomography (OCT) (selected sites)

Anterior segment OCT will be performed at selected sites at Visit 2, 6, 7 to assess epithelial thickness (uM) of central, superior, temporal, nasal, and inferior zones; Stromal Thickness (μ M) in the NEI Central Zone, presence/absence of Epithelial surface irregularities, Persistent Epithelial Defect (PED), Scarring of Stroma, Stromal Thinning, Descemet's Membrane Folds, and Corneal Ulceration

1.3.3.9 Confocal microscopy (selected sites)

Confocal microscopy will be performed at selected sites at Visit 2, 6, 7. Structural nerve regeneration (density, length, nerve density, tortuosity) will be assessed by a reading center to be determined.

1.3.4 Safety Assessments

1.3.4.1 Adverse events

Adverse events (AEs) will be collected and recorded for any untoward event that occurs in a patient from the time he or she signs the ICF for the trial until 24 weeks after the last dose of Study Product. Thus, any untoward medical occurrences or unfavorable and unintended signs, symptoms, or diseases that occur in the pretreatment, treatment, or post treatment period are to be considered AEs and/or SAEs, and consequently recorded and reported as such. Should a non-serious AE become serious, the Investigator will then follow the same reporting procedures as for SAEs. Each AE will be recorded for duration

Confidential

Final Version 1.0, 2021-05-20

(start and stop dates), severity, relationship to the study drug, action(s) taken, outcome.

1.3.4.2 Intraocular Pressure

Intraocular Pressure (IOP) measurements (mmHg) will be performed by Goldmann applanation tonometry with a single measurement at visit 1, 2, 6, 7.

1.3.4.3 Slit Lamp Examination

Slit Lamp Examination will be performed to assess lashes, eyelids, conjunctiva, cornea, lens, sclera, iris, and anterior chamber at visit 1, 2, 4, 6, 7 based on following categories: Normal, Abnormal Non-Clinically Significant, Abnormal Clinically Significant.

1.3.4.4 External Ocular Examination

The motility of the extraocular muscles and the appearance and function of the eyelids will be assessed at Visit 1, 2, 4, 6, 7, and recorded as: Normal, Abnormal Non-Clinically Significant, Abnormal Clinically Significant.

1.4 Study Data

The study data to be analyzed include all clinical data captured by eCRF, as well as external data per data transfer agreements. The eCRF database will be locked for the final analyses.

2 GENERAL ANALYSIS DEFINITIONS

All analysis dataset preparations and statistical analyses will be performed using SAS[®] version 9.4 (SAS/STAT 15.1) or higher. Listings for CSR Appendix 16.2 will include, as a minimum, all the subject data points to be used for analyses. Data listings will be provided for all subjects with data available.

2.1 Study Eye

Based on the protocol, the study eye is the eye at Visit 2 having Grade 3 FCS per the NEI scale in the central zone and a decreased corneal sensitivity (≤ 4 cm using the Cochet-Bonnet aesthesiometer) in the central zone at both Visit 1 and Visit 2. If both eyes have a qualifying central zone meeting FCS and corneal sensitivity requirements at both Visit 1 and Visit 2, the right eye will be selected as study eye. If both eyes meet the FCS and corneal sensitivity requirements in the central zone, the subject will be treated bilaterally. If only one eye qualifies, but the contralateral eye has FCS in the central zone ≥ 2 on NEI scale and the Investigator feels that both eyes would benefit from treatment (i.e. the qualifying eye is abnormal, but does not meet criteria for study) both eyes may be treated with study product. Data will be collected and recorded in the eCRF for both eyes throughout the study. If there is only one qualifying eye/one study eye, only one eye will be treated; however, both eyes will be evaluated, and data will be collected for both eyes.

Confidential

Final Version 1.0, 2021-05-20

2.2 Treatment Group

All the analyses will be conducted based on a single treatment group, which is labelled as "cenegermin-bkbj 0.002%".

2.3 Study Period, Visit, and Day

The overall study consists of initial Screening, a 14-day Washout Period, an 8week Treatment Period, and a 24-week Follow-up Period.

A reference date refers to the date of the first study product administration. All safety and efficacy assessments at all visits will be assigned a day relative to this date. The relative day will be defined as: visit date – reference date + 1 for visits on or after the reference date, and visit date – reference date for visits before the reference date.

2.4 Definition of Baseline

In general, the baseline is defined as the last assessment before the first study product administration unless specifically stated otherwise. Ocular measurements will use the most recent measurement for each eye.

2.5 Out of Window and Unscheduled Visits

All scheduled assessments after first administration of randomized study product will be used. The protocol defined windows for scheduled visits will not be used in the analyses by visit. Data will be assigned to the scheduled visit closer in time to the scheduled visit. Unscheduled visit data will only be used in an analysis if there is no other available data closer in time to a scheduled visit. Post first dose unscheduled assessments will be taken into account for worst-case determination as applicable. All unscheduled visit data will be included in data listings.

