carton. Patients should be instructed to try and complete therapy before last treatment appointment, so at time of end of treatment evaluation the patient should have completed the six times a day dosing on Day 56/Week 8 for Visit 6. This will require PIs and their staff to try and schedule the last visit at the end of the day, so the patient has sufficient time to complete 6 doses on the day of Visit 6.

- 6.1.6. Visit 6 (Day 56/Week 8 4 days): END OF TREATMENT OR PREMATURE DISCONTINUATION VISIT
 - 1. IDEEL
 - 2. EQ-5D-5L
 - 3. *Pregnancy Test for women of childbearing potential: Perform a urine pregnancy test and record the results
 - 4. *Concomitant Ocular and Systemic Medications Update
 - 5. *Record AE's
 - **6. Ophthalmic Examinations:** The following examination/procedures will be performed on BOTH EYES unless otherwise specified:
 - a. BCDVA
 - b. External Ocular Examination
 - c. Slit Lamp Examination
 - d. Corneal Photo Without Fluorescein
 - e. Instill Fluorescein
 - f. TFBUT
 - g. Corneal Fluorescein Staining
 - h. Corneal Photo with Fluorescein
 - i. Wait 10 minutes before performing Schirmer Test
 - j. Corneal Sensitivity
 - k. Schirmer Test Without Anesthesia (Schirmer I)
 - l. IOP
 - m. Anterior Segment OCT (selected sites)

- n. Confocal Microscopy (selected sites)
- 7. Collect used Study Product and Subject Dosing Diary
- 8. Dispense Daily Study Dosing Diary
- 9. Dispense Systane®
- 6.1.7. Visit 7 (Day 224/Week 32 ±7 days): FOLLOW-UP/FINAL STUDY VISIT
 - 1. IDEEL
 - 2. EQ-5D-5L
 - 3. *Concomitant Ocular and Systemic Medications Update
 - 4. *Record AE's
 - **5. Ophthalmic Examinations**. The following examination/procedures will be performed on BOTH EYES unless otherwise specified:
 - a. BCDVA
 - b. External Ocular Examination
 - c. Slit Lamp Examination
 - d. Corneal Photo Without Fluorescein
 - e. Instill Fluorescein
 - f. TFBUT
 - g. Corneal Fluorescein Staining
 - h. Corneal Photo with Fluorescein
 - i. Wait 10 minutes before performing Schirmer Test
 - j. Corneal Sensitivity
 - k. Schirmer Test Without Anesthesia (Schirmer I)
 - l. IOP
 - m. Anterior Segment OCT (selected sites)
 - n. Confocal Microscopy (selected sites)

- 6. *Collect Daily Study Dosing Diary
- 7. Patient will be discharged from the study

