5 ANALYSIS OF EFFICACY

5.1 Primary Efficacy Variable

The primary efficacy variable is the achievement of epithelial healing at Visit 6/Week 8, which is defined as Grade 1 or absence of staining (Grade 0) in the central qualifying zone of study eye via FCS (per NEI scale). The primary efficacy variable will be summarized as a binary goal attainment variable (Yes/No).

The primary analysis will be based on observed cases (i.e. no missing data imputation). As a sensitivity analysis, the last post baseline observation prior to Week 8 will be carried forward for imputing missing data at Week 8. In addition the worst post baseline observation prior to Week 8 will be carried forward for imputing missing data at Week 8 and patients who took any rescue medication prior to Week 8 will be considered as a treatment failure (not epithelial healed) at Week 8.

All summaries and analyses for the primary efficacy variable will be presented for both FAS and FTS populations.

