5.2 Secondary Efficacy Variables

All the analyses of secondary efficacy variables will be performed based on the observed cases in the FAS population. No missing data imputation will be considered.

• Percentage of patients who experienced epithelial healing at 4 weeks

The patients who experienced epithelial healing at Visit 4/Week 4 will be determined for study eye similarly as the primary efficacy variable. It will be summarized as a binary goal attainment variable (Yes/No).

• Percentage of patients who achieved epithelial healing at Week 8 and remained healed throughout the follow-up period

The patients who achieved epithelial healing at Week 8 and remained healed throughout the follow-up period will be determined for study eye at Visit 7/Week 32 similarly as the primary efficacy variable. It will be summarized as a binary goal attainment variable (Yes/No) based on the subset of patients who achieved epithelial healing at Week 8, as well as based on the FTS.

• Percentage of patients who experienced complete healing at Week 4 and 8

The patients who experienced complete healing at Week 4 and 8 will be determined for study eye by the investigator and recorded on eCRF. The complete healing is defined as Grade \leq 1 in the central qualifying zone of study eye via FCS (per NEI scale) and no persistent staining in the non-qualifying zones (excluding the superior zone) defined as the absence (Grade 0) of pathological staining via corneal photography. It will be summarized as a binary goal attainment variable (Yes/No).

• Percentage of patients who achieved complete healing at Week 8 and remained completely healed throughout the follow-up period

The patients who achieved complete healing at Week 8 and remained healed throughout the follow-up period will be determined for study eye at Visit 7/Week 32 by the investigator and recorded on eCRF. It will be summarized as a binary goal attainment variable (Yes/No) based on the subset of patients who achieved complete healing at Week 8, as well as based on the FTS.

• Mean change in corneal sensitivity from baseline at 4, 8, and 32 weeks

The corneal sensitivity (cm) in the NEI zone of the study eye as measured by the Cochet-Bonnet aesthesiometer will be summarized as a continuous variable.

• Percentage of patients that achieve an improvement in corneal sensitivity at 4, 8, and 32 weeks

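### SAP 2.5 assigns data to the nearest visit with no maximum distance, so an exam as late as Day 139 can supply the Week 8 response and one from Day 141 could supply the Week 32 durability result

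*SAP*

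**What the plan says.** SAP 2.5 sets the protocol windows aside: "The protocol defined windows for scheduled visits will not be used in the analyses by visit". In their place, "Data will be assigned to the scheduled visit closer in time to the scheduled visit". Unscheduled exams are held back by one condition: "Unscheduled visit data will only be used in an analysis if there is no other available data closer in time to a scheduled visit". The section gives no maximum distance and no rule for ties.

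Two endpoints depend on this mapping. Under SAP 5.1, "The primary efficacy variable is the achievement of epithelial healing at Visit 6/Week 8", analysed on observed cases. For durability, SAP 5.2 says that Week 8 healers who "remained healed throughout the follow-up period will be determined for study eye at Visit 7/Week 32 similarly as the primary efficacy variable"; this too is analysed without imputation, in those healers and on the Full Treated Set.

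The schedule (Protocol section 2 and SAP Appendix 1) puts Visit 6 at Day 56 with a window of minus 4 days and Visit 7 at Day 224 ± 7 days, with nothing between them. Protocol 3.3 allows unscheduled visits during follow-up. Under Protocol 6.2, patients who discontinue prematurely have the Visit 6 procedures, which include fluorescein staining, and are then off study.

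**The concern.** Nearest-visit assignment is a reasonable way to keep data when visits are close together. Here it has to bridge a gap of 168 days. The primary endpoint is meant to describe the eye at the end of eight weeks of dosing, and the durability endpoint is meant to describe 24 weeks off product. Under the stated rule, an exam made weeks after the last dose can stand as the end-of-treatment response. By then the patient may be using artificial tears or, if not completely healed, other topical treatment. An exam made about halfway through follow-up could stand as the Week 32 result.

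The imputation rules do not catch this. The two sensitivity analyses in SAP 5.1 carry an earlier value forward only when Week 8 is missing. Once a late exam has been mapped to Week 8, the value is no longer missing.

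The trial has one arm and no hypothesis test, so the percentages and their exact intervals are the efficacy result, and no control arm would share a distortion.

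**Working it through.** **The plan's own figure.** Protocol 9.1 gives lower 95% limits of 40% and 54% for healing rates of 58% and 72% in 35 evaluable patients. The Clopper-Pearson lower limit with x = 35 × rate is 40.2% and 54.3%, so the figures reproduce. The point does not depend on them, but the same interval is used below.

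**Day scale.** SAP 2.3: "A reference date refers to the date of the first study product administration". Dosing starts the day after Visit 2, so relative Day 1 is protocol Day 1 and eight weeks of dosing end on Day 56.

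**Boundary.** The midpoint of Visits 6 and 7 is (56 + 224)/2 = 140.

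| Visit | Protocol window | Days captured by SAP 2.5 |
|---|---|---|
| Week 8, all post-dose visits as targets | Days 52–56 (5 days) | Days 50–139 (90 days) |
| Week 8, only visits with staining as targets | Days 52–56 (5 days) | Days 43–139 (97 days) |
| Week 32 | Days 217–231 (15 days) | Day 141 onward, no upper limit |

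Day 140 is an unresolved tie. If Week 8 and Week 32 were read as relative Days 57 and 225, the bounds would move by one day, to 140 and 142.

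- Latest Week 8 value: 139 − 56 = 83 days after planned dosing ends.
- Earliest Week 32 value: 141 − 56 = 85 of 168 follow-up days (51%), and 224 − 141 = 83 days before the target.

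**What happens to each kind of follow-up exam, given an on-time Visit 6 and no later exam**

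- Healed exit or unscheduled exam from Day 141: nearest to Week 32, so it could count as durable.
- Relapse exit on Days 57–139: nearest to Week 8, where the on-time value is closer. The patient has no Week 32 value and can leave the observed cases.
- Relapse exit from Day 141: nearest to Week 32, so it would normally count as not healed.

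**Effect of one patient.** Take 25 of 35 healed at Week 8 (71.4%, the whole count nearest to 72%). For durability, assume for illustration that 20 of those 25 stay healed.

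- Week 8, late healed patient treated as missing: 24/34 = 70.6%, a shift of 0.8 points. In general the shift is (1 − p)/(n − 1) = 0.286/34 = 0.0084.
- Week 8, late non-healed patient treated as missing: 25/34 = 73.5%, up 2.1 points.
- Week 8, late healed patient counted as a failure: 24/35 = 68.6%, a shift of 1/35 = 2.9 points.
- Durability, early healed exit treated as missing: 19/24 = 79.2% against 80.0%, a shift of 0.2/24 = 0.8 points.
- Durability, the same patient counted as a failure: 19/25 = 76.0%, a shift of 1/25 = 4 points.

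**Effect on the exact lower limit at Week 8** (53.7% at 25/35)

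| Late-assessed healers | Treated as missing | Counted as failures |
|---|---|---|
| 1 | 52.5% | 50.7% |
| 2 | 51.3% | 47.8% |
| 3 | 50.0% | 44.9% |

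The numbers of patients in this table are assumptions.

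**The case against.** Several things limit the reach of the rule. An unscheduled exam enters only if nothing closer to the scheduled visit exists, so a patient with an on-time Visit 6 keeps that value. Day 139 is the arithmetic extreme, and nothing in the documents suggests how often exams would fall so late. The primary result is also shown on the Full Treated Set, which requires treatment through Visit 6; a patient whose supply ran out weeks before a late Visit 6 arguably fails that wording. All efficacy analyses are declared exploratory. These limits stand, but none is a cap: the Full Analysis Set result has no such filter, and the Full Treated Set wording does not settle the case.

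A reader might infer that an exit exam from Day 141 is certainly credited as Week 32 healing. The documents do not go that far. The exit exam uses Visit 6 procedures, SAP 1.3.3.1 has healing recorded at Visits 4, 6 and 7, and the complete-healing version of durability rests on an investigator entry. The mapping is possible under SAP 2.5 but is not spelled out.

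A reader might also infer that the error always favours the product. For durability, an early healed exit and a lost early relapse both would. But Protocol 3.3 requires discontinuation for deterioration during follow-up, and under the present rule a relapse exit from Day 141 is counted as not healed. At Week 8, a late exam could show relapse as easily as healing. The net direction is therefore open.

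**Conclusion.** The gap is real and should be closed. SAP 2.5 has no maximum distance, and across the Day 56 to Day 224 gap it can put an off-product exam into the primary Week 8 response, could credit durability after about half of follow-up, and can lose early relapses from the observed cases. The Week 8 consequence needs a missed or late Visit 6. The durability credit needs a healed exam from Day 141 with no exam closer to Day 224.

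The size per patient is modest under the plan's own observed-case analysis: about 0.8 points for a healed patient at 25/35, and about 0.8 points for durability at an assumed 20/25. A reader might take each such patient to be worth 2.9 or 4 points, but that holds only if the patient is counted as a failure, and the SAP does not say that missing values count as failures. The number of patients affected cannot be derived from the documents.

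**What to change.** Keep nearest-visit assignment and add a two-sided cap to SAP 2.5, for example Week 8 = Day 56 ± 7 days (Days 49–63) and Week 32 = Day 224 ± 14 days (Days 210–238). The widths are the sponsor's choice and should be set before database lock; these examples are wider than the protocol windows. The lower bound at Week 8 is needed because the present rule also admits exams from Day 43 or Day 50. The SAP should also say that only visits at which the assessment is scheduled serve as targets. The cap then removes the Day 140 tie.

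Two statements should go with it:

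1. An assessment outside these windows cannot supply a Week 8 response or durable healing at Week 32.
2. Any documented loss of healing after Week 8, at an unscheduled or exit exam on any day, counts as not remaining healed.

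The second is essential. With the cap alone, a relapse exit on Days 141–209 would fall outside the Week 32 window and drop out of the observed cases, although the present rule counts it as a failure.

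The cost is a few sentences in the SAP and a few more missing Week 8 or Week 32 values. No visit, dose or assessment changes.

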2.6 Analysis Populations

A summary table of number (%) of patients in each analysis population/set will be provided.

2.6.1 Screened Population

The Screened Population will consist of all patients who attended Screening, signed the informed consent form, and were assigned a patient identification number.

2.6.2 Enrolled Population

The Enrolled Population (ENRL) will consist of all patients who signed the informed consent form and attended Visit 2.

2.6.3 Full Analysis Set

The full analysis set (FAS) will include all enrolled patients who received at least one dose of study drug. The FAS will be used also for safety analyses.

2.6.4 Full Treated Set

The full treated set (FTS) will include all enrolled patients who received treatment of study drug through Visit 6.

2.7 Unit of Analysis

In general, the unit of analysis will be study eye (affected eye) for eye-level summary, and subject for subject-level summary. Data for both eyes will be presented in the data listings.

2.8 Definition of Subgroups

No subgroup analyses are planned.

2.9 Descriptive Summaries

Summary statistics and statistical analyses will generally be performed only for subjects included in the relevant analysis population. For the calculation of summary statistics and statistical analysis, unrounded data will be used. For endpoints that are continuous in nature: number of observations, mean, median, minimum and maximum, and standard deviation (SD) values will be presented as descriptive statistics summary for both observed values and change from baseline values at each scheduled visit if applicable. For endpoints that are categorical in nature: frequency counts and percentages will be presented as descriptive statistics summary at each scheduled visit if applicable.

The number of decimal places to display for calculated data will be determined by the original scale of the data. Means and medians will be reported with one (1) additional decimal place. Standard deviation will be reported with two (2) additional decimal places. Minimum and maximum will be reported with the same number of significant digits as the method of capture.

